Before surgery, 20-gauge venous access will be established in all patients, and infusion with 2-4 mL/kg/h ringer's acetate solution will be started, general anesthesia will be induced with IV injection of fentanyl (1.5 µg/kg) (*Plaud et al., 2020*), propofol (2 mg/kg) (*Gelberg et al., 2014*) and atracurium (0.5 mg/kg) (*Plaud et al., 2020*) in the same sequence. Endotracheal intubation will be performed, controlled mechanical ventilation will be maintained to keep the end-expiratory carbon dioxide (CO₂) values between 34 and 36 mmHg using capnography. Anesthesia will be maintained with isoflurane 1-2 MAC in 40 % oxygen in air. Incremental dose of atracurium (0.1 mg/kg) (*Bhoi et al., 2019*) will be given after assessment by nerve stimulator according to train of four. Granisetron 3mg (*Dehghanpisheh et al., 2022*) (EM-EX[®] ,3mg/3ml, Amoun pharmaceutical company, Cairo, Egypt) will be also administered to prevent postoperative nausea and vomiting.

Intraoperative fentanyl 0.5 µg/kg (*Plaud et al., 2020*) will be given if the HR or the blood pressure or both increase by >20% of the baseline. At the end of the procedure Isoflurane will be discontinued, neuromuscular blockade will be antagonized by using neostigmine 0.04 mg/kg (*Choi et al.,*

2016) plus atropine 0.01 mg/kg (*Elnasr et al., 2019*) after assessment by nerve stimulator according to train of four and will be administered to reverse the effect of atracurium. After extubation, all patients will be transferred to the post-anesthesia care unit (PACU).

- **Postoperative settings:**

During the first 24 hr after surgery, Postoperative pain will be evaluated by VAS score at 0 point (on admission to the PACU), 2, 4, 8, 16 and 24 hours postoperatively and increments of intravenous meperidine 0.5 mg/kg (*Friesen et al., 2016*) (pethidine-HCL®, 50 mg/ml, Misr company for pharmaceuticals, Cairo, Egypt) will be given as a rescue analgesia at any time the patient feels any pain for a pain score more than 4 (maximum dose 600 mg per day) (*Friesen et al., 2016*), if the patient still in pain after using maximum dose meperidine per day, she will be given morphine 0.1 mg/kg (*ElGhamry and Amer, 2019*) (Morphine sulphate®, 10 mg/ml, Misr company for pharmaceuticals, Cairo, Egypt), considered block failure to be excluded from the study and replaced by another patient to fulfill sample size criteria.

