In the presence of nausea, with or without vomiting, granisetron 3 mg (*Gelberg et al., 2014*) will be given IV and repeated once if nausea persisted (maximum dose of 6 mg per day) (*Gelberg et al., 2014*).

- Complications after puncturing of the blockade (hematoma in the puncture sites, pneumothorax, bradycardia defined as heart rate (HR) <50 beats/min, tachycardia defined as HR >110 beats/min, hypotension defined as a decrease in mean arterial pressure (MAP) of >20% from the baseline value and hypertension defined as an increase in MAP of >20% from the baseline value) will be evaluated and well-managed.

- **Outcome measurement:**

The age, weight, height, the American Society of Anesthesiologists (ASA) class of each patient will be recorded and compared among both groups.

- **Primary outcome:**

Post-operative pain severity assessed by VAS at 0 point (on admission to the PACU).

- **Secondary outcomes:**

1. Post-operative pain severity assessed by VAS at 2 hr, 4 hr, 8hr, 16 hr

and 24 hr.

2. Time of first rescue analgesia.
3. Cumulative post-operative meperidine consumption in the first 24 hours.

➤ **Statistical Analysis:**

All data will be recorded, analyzed and statistically compared between both groups to describe the groups and identify any significant differences between them. The quantitative data will be presented as mean \pm standard deviation and range. Qualitative data will be presented as a number and percentage. Non-parametric data will be presented as a median and inter-quartile range.

The following tests will be done:

- Independent samples t-test of significance will be used when comparing between two means.
- Mann Whitney U test: for two-group comparisons in non-parametric data.
- Chi-square (χ^2) test of significance will be used in order to compare proportions between qualitative parameters.
- The confidence interval will be set to 95% and the margin of error accepted will be set to 5%. So, the p-value will be considered significant as the following:
 - P-value <0.05 will be considered significant.
 - P-value <0.001 will be considered as highly significant.
 - P-value >0.05 will be considered insignificant.

➤ **Statistical package:**

Recorded data will be analyzed using the statistical package for social sciences, version 23.0 (SPSS Inc., Chicago, Illinois, USA).

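### Time of first rescue analgesia has no rule for a patient not rescued by 24 hours; leaving such patients out can hide part or much of a real difference, depending on how many there are

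*Combined protocol and SAP*

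**What the plan says.** All references are to the combined protocol and SAP.

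Outcome measurement lists "Time of first rescue analgesia" as the second of three secondary outcomes. It gives no start of the clock, no end of follow-up, and no definition for a patient who needs no rescue.

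Methodology, Postoperative settings, decides when the event can occur. Meperidine "will be given as a rescue analgesia at any time the patient feels any pain for a pain score more than 4". The same paragraph sets the follow-up: "During the first 24 hr after surgery, Postoperative pain will be evaluated by VAS score at 0 point (on admission to the PACU") and then at fixed hours up to 24.

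Statistical Analysis offers two routes for a quantitative outcome. One is "Independent samples t-test of significance will be used when comparing between two means". The other is "Mann Whitney U test: for two-group comparisons in non-parametric data", with the reporting rule "Non-parametric data will be presented as a median and inter-quartile range". It does not say which route this outcome takes, and it mentions no censoring, Kaplan-Meier curve or log-rank test.

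The only rule that removes patients after treatment concerns the opposite kind of patient, the one with the most rescue. In Postoperative settings, "if the patient still in pain after using maximum dose meperidine per day", she receives morphine and is "considered block failure to be excluded from the study and replaced by another patient to fulfill sample size criteria".

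**The concern.** A patient whose score never passes 4 within 24 hours has no rescue time. Both listed tests need a number or a rank from each patient, and the plan supplies neither. Three readings remain open:

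- Her cell is left blank and she drops out, so only patients who needed rescue are compared. The block that works longer then loses its best results.
- 24 hours is entered and a mean is reported. Called the mean time to rescue, that figure is too short.
- She is ranked as tied longest. This is valid, because every patient has the same 24-hour window, but it is not written down.

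The readings can give different verdicts, and the choice could be made after the data are seen. Unrescued patients are plausible: the Sample Size section expects median VAS scores of 1 (1-2) and 2 (1-3) at 1 hour, well under the threshold. That is early pain only and does not fix the share rescued by 24 hours.

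The block-failure rule raises a related matter. It selects on a result that arises after randomisation, and it discards patients whose first rescue time is known.

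**Working it through.** **The plan's own figure.** There is none to reproduce. The 10 per group rests on VAS, and the documents state no rescue share, rescue time or effect for this outcome.

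**Inputs.** From the documents: 10 per arm, a 24 h window, alpha 0.05. Assumed: exponential times to rescue and a hazard ratio of 0.5 in favour of one block, across a range of rescued shares.

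**Means.** Let p be the share rescued by 24 h and L = -ln(1-p)/24. The restricted mean (24 h counted for the unrescued) is p/L. The mean among rescued patients only is 1/L - 24(1-p)/p.

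- At 55 v 80% rescued:
  - p = 0.80 gives 1/L = 14.91 h, a restricted mean of 0.80 x 14.91 = 11.9 h and a rescued-only mean of 14.91 - 6.00 = 8.9 h.
  - The other arm has 1-p = √0.20 = 0.447, so 1/L = 29.82 h, a restricted mean of 16.5 h and a rescued-only mean of 10.4 h.
  - Dropping keeps 1.5 of 4.6 h, or 33%.
- At 90 v 99% rescued: 7.76 v 4.97 h among the rescued, against 9.38 v 5.16 h restricted. Dropping keeps 2.8 of 4.2 h, or 66%.

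**Chance that the question arises.** P(at least one unrescued among 20) = 1 - pA^10 x pB^10. At 90 v 99% this is 1 - 0.349 x 0.904 = 69%.

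**Rejection rates.** These come from 20,000 simulated trials per scenario. Both Mann-Whitney readings use the tie-corrected normal approximation without continuity correction. Trials with fewer than two rescued patients in an arm count as non-rejections for the dropped reading.

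| Rescued by 24 h | Difference kept if dropped | Any unrescued | Dropped | Tied Mann-Whitney | Log-rank | Dropped and tied verdicts differ |
|---|---|---|---|---|---|---|
| 37 v 60% | 25% | about 100% | 5% | 17% | 19% | 19% |
| 55 v 80% | 33% | about 100% | 6% | 21% | 25% | 21% |
| 78 v 95% | 49% | 95% | 11% | 24% | 30% | 17% |
| 90 v 99% | 66% | 69% | 16% | 25% | 32% | 10% |
| 97 v 99.9% | 83% | 28% | 22% | 25% | 31% | 4% |

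At hazard ratio 0.7 the share kept is 27% to 74%, and rejection is 5-9% dropped, 9-11% tied and 9-13% log-rank.

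**No true difference.** Choosing the better of dropped and tied after seeing the data rejects in 6.5% to 8.8% of trials (30% to 95% rescued), not 5%. Null rejection is 4.6-5.3% for tied Mann-Whitney and 4.6-6.7% for log-rank, so part of the log-rank advantage is slight liberality.

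**Other time distributions.** In a separate run of 2,000 trials per scenario with Weibull shape 2, medians of 4 v 8 h leave almost no one unrescued, and dropping costs nothing (66% under both readings). Medians of 8 v 16 h leave about 21% of the longer arm unrescued, and rejection is 42% dropped against 67% tied.

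**Block failures.** At an assumed 60 to 80 kg, reaching 600 mg in 0.5 mg/kg steps takes 600/(0.5 x 60) = 20 down to 600/(0.5 x 80) = 15 doses, so failures may be rare. Suppose one in ten of an arm with 80% rescued failed. Excluding them raises that arm's restricted mean from 11.9 h to (0.7 x 8.91 + 0.2 x 24)/0.9 = 12.3 h if failures are random among the rescued, or to at most 13.2 h if they are the earliest rescued. With no failures the effect is nil.

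**The case against.** The strongest reply is that the loss depends on a choice the plan never makes. A reader might infer that never-rescued patients will be dropped. No section says so, and Statistical Analysis opens by stating that all data will be analysed. This stands: dropping is what happens by default with a blank time, not a stated intention.

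A reader might also infer that the listed tests are unusable, or that a mean with 24 h entered is an error. Neither follows. Mann-Whitney with unrescued patients tied longest is sound. A t-test with 24 h entered rejects in 16% to 29% of trials across the five hazard ratio 0.5 scenarios, much like tied Mann-Whitney, with null rejection of 4.3-5.6%. Since everyone shares the same window, that mean is a legitimate restricted mean, provided it is labelled as one. Log-rank is therefore one option and not a necessity.

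A third tempting inference is that power is low whichever rule is used. That holds only for the exponential scenarios at hazard ratios 0.5 and 0.7. With Weibull shape 2, tied Mann-Whitney reaches 66-68% for a doubling of the median at 4 v 8, 6 v 12 or 8 v 16 h, and about 95% at 8 v 24 h.

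Finally, the block-failure rule excludes patients from the whole study, so it is wider than this outcome, and the one-in-ten failure rate is invented for illustration. Both points stand. What the reply does not remove is the missing rule itself.

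**Conclusion.** The concern holds in a conditional form. The outcome is a time to event with a fixed 24 h horizon, and the plan does not say what a never-rescued patient contributes to the tests it lists. If she is dropped, 25% to 83% of the 24 h restricted-mean difference survives in the assumed exponential scenarios at hazard ratio 0.5, and the chance of detecting the difference falls most when many are unrescued. The loss is nil if everyone is rescued and can be nil under other time distributions. The true size cannot be fixed, because the documents give no rescued share.

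The never-rescued gap is confined to this secondary outcome. The primary outcome, VAS on PACU admission, is unaffected by it, and a never-rescued patient has a natural value of 0 mg for cumulative meperidine. The same cannot be said of block-failure exclusion, which takes those patients' data out of every outcome, the primary included. Its size is unknown and may be nil. The plan should be amended on both points, but neither shows that its listed tests are wrong.

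**What to change.** Add to Statistical Analysis, before any data are seen:

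- Time to first rescue runs from PACU admission (the plan's 0 point) to the first rescue dose.
- One of two rules, chosen now. Either censor never-rescued patients at 24 h and report Kaplan-Meier curves, the median or a statement that it was not reached, and a log-rank test; or keep the listed Mann-Whitney test with never-rescued patients ranked as tied longest.
- Under either rule, report the number rescued by 24 h in each arm.
- Label any mean that has 24 h entered as the mean rescue-free time within 24 h (restricted mean), not as the mean time to rescue.
- Keep the observed first rescue time of every randomised patient, including block failures and their replacements, in the arm to which she was randomised. Apply the same all-randomised set to the other outcomes so that the analysis sets match.

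The cost is a few lines of text, a little more analysis work, and retaining the data of block failures; the total could then exceed 20 patients. Log-rank is slightly liberal at 10 per arm (null rejection up to about 6.7%), which favours the Mann-Whitney option if strict error control matters most. No dose, threshold or clinical rule needs to change.

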Using PASS 15 program for sample size calculation, setting power at 90% and alpha error at 0.05 and according to "***Bakeer & Abdallah, 2022***", the expected median VAS score 1-hour post-operative in PECS II group = 1(1-2) and in ESPB group= 2(1-3). Sample size of 10 patients per group will be needed to detect the difference between two groups.

- **Ethical consideration:**

Patient informed written consent and approval of the Research Ethical Committee of the Faculty of Medicine; Ain Shams University will be obtained before patient's allocation.

- **Study procedures:**

- **Preoperative settings:**

All patients will be assessed preoperatively by careful history taking, full physical examination, laboratory evaluation and other appropriate investigations.

At the preoperative visit, all patients will be instructed on how to evaluate their own pain by using a 10-cm visual analogue pain scale (VAS) (0 = no pain, 10 = maximum pain imaginable).

The nerve block will be performed in the preoperative block area following standardized monitoring, including non-invasive blood pressure (BP), electrocardiogram (ECG), and pulse oximetry (PO). Oxygen 2–3 L/min will be applied through the nasal cannula and IV midazolam 0.025 mg/kg will be given and dose may be repeated every 3–5 minutes until

sedation is adequate and patient still arousable up to 20 mg (*Pedro et al., 2022*). All blocks will be performed by the same two experienced senior attending doctors in ultrasonic-guided nerve blocks. Patients will be randomly divided according to a computer-generated random number table into two groups:

- Group 1 (**PECS II group**): patients will receive ultrasound guided PECS II block (10 patients).
- Group 2 (**ESPB group**): patients will receive ultrasound guided erector spinae plane block (10 patients).

Both blocks will be performed under complete aseptic precautions using ultrasound machine with high-frequency linear probe covered with sterile sheath (Sonosite M-turbo c, Bothell, Washington, USA) and linear ultrasound probe (2.5-7.5MHz) and a 22G 100 mm echogenic needle (B-Braun Medical Inc., Bethlehem, PA, USA) which will be inserted after standard skin disinfection and infiltration of 2 millilitres (mL) lidocaine 2% subcutaneously.

Pre-operative chest ultrasound will be done by the anesthesiologist to detect complications after puncturing of the blockade (hematoma in the puncture site by direct visualization and pneumothorax by Barcode/Stratosphere sign).

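### Seven secondary comparisons are each called significant at P<0.05 with no adjustment or exploratory label, so secondary claims carry a false-positive risk well above 5% (about 30% if the outcomes were independent)

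*Combined protocol and SAP*

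**What the plan says.** Under Outcome measurement in section 3, the protocol names one primary outcome, VAS on admission to the PACU, and three numbered secondary outcomes:

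- "Post-operative pain severity assessed by VAS at 2 hr, 4 hr, 8hr, 16 hr", and also at 24 hours;
- "Time of first rescue analgesia";
- "Cumulative post-operative meperidine consumption in the first 24 hours".

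The Statistical Analysis part states: "All data will be recorded, analyzed and statistically compared between both groups to describe the groups and identify any significant differences between them". The tests it lists are the independent-samples t-test, the Mann-Whitney U test and the chi-square test. It then fixes the interpretation for all results: "P-value <0.05 will be considered significant", with a further grade of 'highly significant' below 0.001.

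The Sample Size paragraph, "setting power at 90% and alpha error at 0.05", is built on a single VAS comparison. Nowhere does the document limit the significance labels to the primary outcome, adjust for the number of tests, set an order of testing, give a method that analyses the repeated VAS scores together, or describe the secondary outcomes as exploratory.

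**The concern.** The first secondary outcome is one line in the list but five comparisons in the analysis. With time to first rescue and meperidine consumption, that gives seven opportunities to declare a difference, under the same label as the primary result.

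This matters because the aim in section 2 is broad: to compare the analgesic efficacies of the two blocks after surgery. The primary outcome is one score at PACU admission, so anything the thesis says about analgesia over the following 24 hours has to come from these seven comparisons. With 10 patients per group, an isolated low P value at one time point would qualify as significant under the plan's own rule, and a reader could not tell it from a chance finding.

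**Working it through.** **Inputs from the protocol.** Threshold 0.05 for every test (Statistical Analysis); 10 patients per group (Sample Size); two-group t-test or Mann-Whitney test (Statistical Analysis); number of secondary comparisons 5 + 1 + 1 = 7 (Secondary outcomes). The primary VAS and the baseline comparisons are not counted.

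**Input that has to be assumed.** The correlation between the seven outcomes. The documents give none, so a range from 0 to 0.9 is used.

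**Step 1: the plan's own figure.** The plan states no error rate for the secondary outcomes taken together; its only figure is 0.05 per test. At 10 against 10, one t-test has a true size of 5.0%. One Mann-Whitney test without ties has a true size of 5.24% with the large-sample P value and 4.33% with the exact P value. The single primary test therefore runs at about its stated 5%.

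**Step 2: seven independent tests, no true difference.** The chance of at least one P<0.05 is 1 − (1 − size)^7:

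- nominal 0.05: 1 − 0.95^7 = 30.2%;
- Mann-Whitney, large-sample P: 1 − (1 − 0.0524)^7 = 31.4%;
- Mann-Whitney, exact P: 1 − (1 − 0.0433)^7 = 26.6%.

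At the nominal 0.05 per test, the chance cannot exceed 7 × 0.05 = 35% under any dependence.

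**Step 3: correlated outcomes.** Trials of 10 against 10 were simulated with no block difference, using seven normally distributed outcomes with a common correlation and at least 20,000 trials per setting (simulation error about 0.3 percentage points). The row for correlation 0 repeats Step 2, except for the whole-number column, which is simulated.

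| Correlation | t-test | Mann-Whitney, large-sample P | Mann-Whitney, large-sample P, whole-number scores | Mann-Whitney, exact P |
|---|---|---|---|---|
| 0 | 30% | 31% | 29% | 27% |
| 0.3 | 27% | 29% | 27% | 25% |
| 0.5 | 23% | 25% | 23% | 21% |
| 0.7 | 19% | 20% | 19% | 17% |
| 0.8 | 16% | 17% | 16% | 15% |
| 0.9 | 12% | 13% | 14% | 11% |

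A common correlation is a simplification. If correlation instead decays along the sequence of outcomes, the t-test figure is 23% when neighbouring outcomes correlate at 0.7 and 20% at 0.8.

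**Step 4: with adjustment.** Under Holm's procedure the smallest of the seven P values is compared with 0.05/7 = 0.00714. If the blocks are equal on all seven outcomes, the chance of any false claim is 1 − (1 − 0.00714)^7 = 4.9% with independent outcomes, and at most 5% under any correlation.

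**The case against.** The strongest reply is that the main inference is already protected. There is one primary outcome, at one time, tested once, and the other results are plainly listed as secondary. Many statisticians would accept unadjusted secondary P values in a 20-patient thesis. This stands in part. Secondary outcomes need no adjustment when they are offered as supportive, but this plan does not offer them that way: it gives them the same labels as the primary. The reply therefore supports an exploratory label as a sufficient remedy. It does not support leaving the rule as written.

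Second, the size of the risk is uncertain, and the independent case is implausible. The VAS scores come from the same patients, and Postoperative settings ties rescue meperidine to a score above 4, so the outcomes must be related. This stands, and it is why about 30% is the upper part of a range rather than the estimate.

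Third, separate testing of the five VAS times is inferred from the list of tests; the plan does not say it outright. That is true, but no listed method could combine the scores.

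A reader might go further and infer that the time-point tests must be replaced by one time-weighted mean VAS, because separate tests waste information. The documents do not support that. The gain depends on a similar block effect throughout the 24 hours, and both groups receive their bupivacaine in a single preoperative session, so a constant difference cannot be presumed. With trapezoid weights of 1, 3, 6, 8 and 4 out of 22, the 2- and 4-hour scores together carry 4/22 = 18% of the summary. Take an assumed effect of 1.2 SD and a correlation of 0.5. If the effect lasts to 8 hours only, power is about 70% for the 2-hour test against about 30% for the summary; if it is constant, the summary has 88%. It is a trade-off, not a correction.

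**Conclusion.** The concern holds for claims drawn from the secondary outcomes. If the blocks are equal, the stated rule produces at least one significant secondary difference in about 30% of such trials with independent outcomes, about 17-20% at correlation 0.7, and about 11-14% at 0.9. The range rests on an assumed correlation, on equal blocks for all seven outcomes, and on each comparison being tested separately. No setting examined brings it near 5%.

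Two further inferences are not supported. One is that the primary conclusion is compromised: its test is single and keeps its own 5%. The other is that a secondary result will decide the verdict on efficacy: nothing in the document says so. The point is that the rule permits such a claim and does not mark it as weaker. This is a cheap improvement rather than a flaw in the main analysis.

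**What to change.** In the Statistical Analysis part of section 3, before the data are examined:

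1. Reserve 'significant' and 'highly significant' for the primary VAS at PACU admission.
2. State that the seven secondary comparisons are exploratory, to be reported as effect estimates with 95% confidence intervals and no significance label.
3. If confirmatory secondary claims are wanted, replace item 2 with Holm's procedure across all seven comparisons, and extend the labels in item 1 only to those that pass it.

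The VAS comparisons at individual time points can stay. No new data, patients or visits are needed. The cost is that some secondary differences can no longer be called significant. Under Holm, the smallest P value would have to be no greater than 0.00714 before any secondary claim could be made, which is demanding with 10 patients per group.
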